2.2 Secondary objectives

1. To obtain preliminary data on the quality of glycemic control among the PC and EN groups, with separate analyses in the IP and TH sub-groups, and in the UC and iLet arms within those groups, which will be used to power a larger study with a glycemic control metric as the primary outcome. Our hypotheses are that glycemic control, with key outcomes being group mean CGM glucose, the group mean time with CGM glucose less than 54 mg/dl, and the group mean time with CGM glucose in the 70–180 mg/dl range, will be similar in the PC-IP group and the EN-IP group, and in the PC-TH group and the EN-TH group in the iLet arm. Additionally, we hypothesize that glycemic control will be similar in the PC-TH group and the PC-IP group, and in the EN-TH group and the EN-IP group in the iLet arm. Further, we hypothesize that there will be a larger difference in glycemic control metrics between the UC arms versus the iLet arm in the PC group than there will be in the EN group.
2. To assess the impact of the insulin-only configuration of the iLet bionic pancreas system on psychosocial outcomes (including quality of life, fear of hypoglycemia, and diabetes distress) among study participants. Secondary analyses will be conducted between the telehealth and in-

person arm, the EN and PC groups, and the iLet and UC arms.

3 Participant Selection

3.1 Inclusion Criteria

1. Age 18-85 years, BMI ≥ 18.5 , have had clinical type 1 diabetes for at least one year, and have taken insulin for at least 1 year
 - a. Prescription diabetes medication regimen stable for > 1 month, including any adjunctive anti-diabetic medications (except for medications that will not affect the safety of the study and are not expected to affect any outcome of the study, in the judgment of the site principal investigator)
 - b. This does not include changes to any insulin doses, including basal rates/long-acting insulin doses, carbohydrate to insulin ratios and correction factors
2. Willing to wear one Dexcom CGM transmitter and sensor (sensor must be changed every 10 days), and one infusion set that must be replaced at least every 3 days.
3. Endocrinology practice criterion is that diabetes is managed using sensor-augmented insulin pump therapy or artificial pancreas therapy for ≥ 3 months)
4. Primary care practice criteria are that diabetes is managed by multiple daily insulin injections (insulin-pump naïve).
5. TH group criterion is that participant must have hardware and internet access capable of 2-way video and audio communication

3.2 Exclusion Criteria

1. Unable to provide informed consent (e.g. impaired cognition or judgment)
2. Unable to safely comply with study procedures and reporting requirements (e.g. impairment of vision or dexterity that prevents safe operation of the bionic pancreas, impaired memory)
3. Unable to speak and read English, as iLet BP support materials and device menus are currently available in English only.
4. Plan to change usual diabetes regimen in the next 3 months including before and during participation in the study
 - a. This would include changing from MDI to pump or from pump to MDI, and starting a CGM if not previously used
 - b. This would not include changes to any insulin doses, including basal rates/long acting insulin doses, carbohydrate to insulin ratios and correction factors
5. Current use of non-FDA approved closed-loop or hybrid closed-loop insulin delivery system (e.g. "Loop" or "Open APS")
6. Unwilling to switch to lispro or aspart for the duration of the study's iLet arm (e.g. from Fiasp or Lyumjev)
7. Known hemoglobinopathy (sickle cell trait is not an exclusion)
8. Current participation in another diabetes-related clinical trial, has a medical condition, or use of a medication that, in the judgment of the investigator, could compromise the results of this study or the safety of the participant
9. History of diabetes due to cystic fibrosis, pancreatitis, or other pancreatic disease, including pancreatic tumor or insulinoma, or history of complete pancreatectomy
10. Have a history of intermittently required glucocorticoid treatment (e.g., but not limited to, for the treatment of asthma, inflammatory bowel disease).

11. A1c >11.0% (most recent value up to 1 year prior acceptable; if none available or >1 year prior, participant will be instructed to obtain A1c through their usual care provider and to make copy of result available to study team)
12. History of diabetic ketoacidosis (DKA) within the past month
13. Electrically powered implants (e.g. cochlear implants, neurostimulators) that might be susceptible to RF interference
14. Established history of allergy or severe reaction to adhesive or tape that must be used in the study
15. Currently treated with GLP-1 analogue, thiazolidinedione (TZD), sulfonylurea, pramlintide, or SGLT-2 inhibitor medication (*use more than 3 months prior to enrollment is acceptable*)
 - a. If using metformin, participants:
 - i. Must be on a stable dose for 1 month prior to enrollment
 - ii. Metformin can be continued while the iLet is used
16. Pregnant (positive urine HCG), breast feeding, plan to become pregnant in the next 6 months, or premenopausal participants who are sexually active without use of contraception
17. Renal failure on dialysis or chronic renal disease with a GFR or eGFR <30mL/min (values within the last two years will be accepted; if none available or >2 years prior, participant will be instructed to obtain GFR or eGFR through their usual care provider and to make copy of result available to study team)
18. Any condition that, in the opinion of the site principal investigator, could interfere with the safe or effective completion of the study.
 - a. Conditions to be considered by the investigator may include, but are not limited to, the following:
 - i. Alcohol or drug abuse
 - ii. Use of prescription drugs that may dull the sensorium, reduce sensitivity to symptoms of hypoglycemia, or hinder decision making during the period of participation in the study
 - iii. Coronary artery disease that is not stable with medical management, including unstable angina, angina that prevents moderate exercise (e.g. exercise of intensity up to 6 METS) despite medical management, or within the last 12 months before screening, a history of myocardial infarction, percutaneous coronary intervention, enzymatic lysis of a presumed coronary occlusion, or coronary artery bypass grafting
 - iv. Known history of prolonged QTc interval, malignant arrhythmia, or congenital heart disease
 - v. Congestive heart failure with New York Heart Association (NYHA) Functional Classification III or IV
 - vi. History of TIA or stroke in the last 12 months
 - vii. Untreated or inadequately treated mental illness
 - viii. History of eating disorder within the last 2 years, such as anorexia, bulimia, or diabulimia or omission of insulin to manipulate weight
 - ix. History of intentional, inappropriate administration of insulin leading to severe hypoglycemia requiring treatment
19. Employed by, or having immediate family members employed by Beta Bionics, or being directly involved in conducting the clinical trial, or having a direct supervisor at place of employment who is also directly involved in conducting the clinical trial (as a study investigator, coordinator, etc.);

or having a first-degree relative who is directly involved in conducting the clinical trial
20. Unable to avoid hydroxyurea for duration of study (interferes with accuracy of Dexcom G6 CGM)

3.3 Source of Participants

Individuals generally will be recruited from each site's existing patient population or from a pool of individuals who contact the site. IRB requirements regarding recruitment materials and policies will be adhered to. Study recruitment methods may consist of the following:

- Culling of pre-existing databases (held by one of the clinical sites or Beta Bionics, Inc.) of patients who have expressed interest in the bionic pancreas or research participation. Those identified will be contacted via IRB-approved mailing sent through post, email blast, or via phone and will be provided information about how to complete the consent process and demographics survey;
- IRB-approved press release announcing study and study fact sheet;
- Support groups, patient education classes, and not-for-profit community support groups (e.g., Children with Diabetes, College Diabetes Network, etc.);
- IRB-approved paper and digital advertisements, brochures, postcards, flyers, and/or newsprint advertisements;
- IRB-approved digital advertisements posted on social media sites like LinkedIn, Twitter, YouTube, Instagram, Facebook, and other public forums managed by a clinical trial site or Beta Bionics, Inc.;
- In-person recruitment and telephone recruitment by individual clinical sites; and
- An IRB-approved website dedicated to clinical trial recruitment.
- Letters/Emails to, phone calls with, or visits with area physicians informing them of the study and asking them to refer any eligible patients who might be interested

All recruitment methods and specific advertising materials will be IRB approved prior to their implementation. No individuals will be excluded based on gender or race. An equal gender distribution is anticipated.

4 Participant Enrollment

4.1 Number of Participants

It is expected that we will have 40 participants complete the study with a consistent protocol, with 20 participants at each site. We estimate that there are, at a minimum, 6700 adults with T1D in Colorado who use MDI, and that there are at least 1100 potential participants who are active patients at just a fraction of the primary care clinics from which we will be recruiting; we therefore expect that recruitment, the experiments, and the analysis can be accomplished over a period of 9-18 months. Up to 80 participants may be screened and enrolled. The upper bound is based on the expectation that some volunteers will be excluded after the screening visit and the possibility that some experiments may have to be discontinued before completion (due to, for instance, intercurrent illness or participant withdrawal).

4.2 Enrollment and Consent Procedures

Prospective participants will be briefed by a study staff member by phone or by e-mail regarding the study procedures and the inclusion and exclusion criteria. Potential participants will be sent an informed consent document by mail, fax or e-mail.

Once potential participants have had time to review the consent document, they will meet with a study

provider (MD or NP) in person, over the phone, or over video conference. They will explain the study, answer any questions, and administer informed consent prior to any data collection or study-specific procedures. If a volunteer is a patient of one of the study MDs or NPs, another staff MD or NP will answer questions and administer consent. A licensed physician investigator will be available to speak with the participants during the consent process in the event of a non-physician administering consent. The site principal investigators will be responsible for assuring that the informed consent process is properly followed and that each study participant is well informed about the study and the participant's responsibilities. Consent will be documented with either electronic or wet ink signatures. Electronic consent will be obtained via REDCap.

Study staff will answer any questions that the participants may have during their participation. They will share any new information in a timely manner that may be relevant to the participant's willingness to continue participating in the trial. The participants may choose to discontinue participation at any time.

5 Study Procedures

5.1 Study Design

This study will assess delivery of the insulin-only iLet bionic pancreas by primary care providers and endocrinologists, as well as delivery of the iLet bionic pancreas via in-person training and support vs telehealth training and support. It will employ a two-center, random-order, two-arm cross-over trial design in a home-use setting in 40 adult participants (18-85 years of age) with type 1 diabetes. This number is based on 10 participants per arm, per site, which has been successfully implemented in previous iLet studies and which has yielded highly significant results in those studies. The two centers will be community-based primary care and academic medical center-based endocrinology. Study participants will be managed by appropriate site-specific study team clinicians: endocrinology providers at MGH, or primary care providers at CU.

The two 14-day study arms will occur in a random-order cross-over design. One arm will involve using the insulin-only iLet bionic pancreas and the other arm will involve insulin delivery via the participants' usual care (multiple daily injections or insulin pump, depending on the study site). Half of the participants will receive care via in-person visits, and the other half will receive care exclusively via telehealth visits. This will result in four study cohorts overall [endocrinology in-person (EN-IP), endocrinology telehealth (EN-TH), primary care in-person (PC-IP), primary care telehealth (PC-TH)].

5.2 Screening Data

- Age
- Sex
- Race and ethnicity
- Basic demographic information
- Date of last menstrual period in pre-menopausal participants
- Approximate date of diabetes diagnosis
- Medical, surgical, and social history, allergies and review of systems relevant to inclusion and exclusion criteria
 - Medical history relevant to T1D diagnosis will also be assessed for information supporting a clinical diagnosis of T1D, which may include: prior diagnosis of T1D, age at diagnosis, symptoms at diagnosis (e.g. DKA), presence of autoimmune markers, family history of

diabetes without type 2 features (e.g. obesity or high-risk ethnicity), body habitus at time of diagnosis, the presence of other autoimmune disorders, low C-peptide levels, as well as any other relevant data in the medical history.

- Medications (prescription and non-prescription) and date of last change in medication regimen
- Duration of insulin pump and CGM use, if applicable
- Type of insulin(s) currently used
- Insulin regimen (basal rate, sensitivity factor, and carbohydrate ratio for pump and if known for MDI; otherwise doses and schedule for MDI, sliding scale/correction if applicable)
- Average total daily dose of insulin in the last 30 days
- Usage of CGM (type of CGM, days per month worn, usage of data, whether insulin dosing is based on CGM alone, alarm settings), if applicable
- Height and weight
- Urine HCG (post-menarchal, pre-menopausal participants)

5.3 Drugs

The study involves subcutaneous administration of **insulin lispro** (Humalog, Lilly) or **insulin aspart** (Novolog, Novo Nordisk). Humalog and Novolog are commercially available by prescription and are indicated for patients with diabetes but are not indicated for use in the iLet bionic pancreas. No participants will use insulin Fiasp during the bionic pancreas arm. Participants using insulin Fiasp as part of their usual care will use insulin aspart with the iLet.

Participants randomized to the UC arm will follow their standard diabetes regimen with the insulin prescribed by their health care provider. During the iLet arm, participants will fill the Ready-to-Fill insulin cartridge with whichever insulin (lispro or aspart) they were using during their usual care, unless using insulin other than lispro or aspart for UC, in which case they will be provided with lispro or aspart for the iLet arm.

The iLet bionic pancreas can administer bolus doses of insulin up to every five minutes. A single automated bolus of insulin will not exceed 3 units per 5-minute dose [30 µl] and a single meal-priming dose, which is triggered by the user, will not exceed 12 units [120 µl].

5.4 Devices

5.4.1 Infusion sets

Participants in the iLet arm will be provided with infusion sets for use with the system. Study staff will work with the participants to ensure they are properly inserting the infusion set and will help them troubleshoot if problems related to the infusion set arise. This will be done in person for EN-IP and PC-IP, and through HIPAA compliant video conferencing software for EN-TH and PC-TH. Participants will be instructed to replace their infusion sets as needed when it fails (or is suspected of failing), falls out, or at least every 3 days. Participants will be given contact information of the study team in the case that they wish to complete the infusion set changes on HIPAA compliant video conferencing software for Healthcare. The number of participants choosing to do this will be tracked.

5.4.2 Continuous glucose monitor (CGM) Sensor

One transcutaneous glucose sensor for the Dexcom G6 CGM will be inserted in the SC tissue and will provide input to the controller. The sensor is powered by the battery within the transmitter that clips to

the sensor. The whole assembly is held to the skin with an adhesive patch and communicates wirelessly via Bluetooth Low Energy with the Dexcom G6 system built into the bionic pancreas. If the G6 sensor fails for any reason during the experiment it will be replaced promptly. The G6 sensor will be replaced at least every 10 days. In the PC group, if the participant is not a CGM user the CGM will be blinded.

5.4.3 *iLet Bionic Pancreas*

The iLet bionic pancreas has an integrated graphical user interface (GUI) and touchscreen display that displays the current CGM glucose, a graphical history of the CGM glucose, and doses of insulin delivered by the control algorithm. The GUI can also be used to input meal announcements, designating qualitatively the meal carb content as “Usual for me”, “More”, or “Less” than usual. This will trigger a partial meal-priming bolus, the size of which will adapt during the course of the trial in accordance with the insulin needs for that size and mealtime (e.g. a portion of the mealtime insulin need).

The target BG for the insulin-only BP is 120 mg/dl by default (“Usual”), but the user may designate a lower default target (of 110 mg/dl, “Lower”) or a higher default target (of 130 mg/dl, “Higher”). Participants transitioning to the BP from an MDI regimen or those who have a very low insulin TDD at baseline may be set to start the study period at the higher glucose target at the discretion of the site investigator. Participants who have a high HbA1c at screening and who may have symptoms of hypoglycemia in the normoglycemic range may be set to start the study period at a higher target at the discretion of the site investigator. Participants will be able to edit their glucose target in all BP arms, but they will be instructed to contact study staff prior to changing their target.

The GUI can also be used to manage meal boluses and correction boluses during periods when the CGM is offline, such as the period after a sensor is replaced and before the new sensor has been calibrated. During these times, the control algorithm will determine and direct the administration of insulin basal rates either based on the participant's weight in the first 24 hours of the experiment, or on the average of adaptively determined basal rates for that time of day once sufficient experience has been accumulated (i.e. 24 hours or more) by the control algorithm. The controller also will administer insulin or decrease basal insulin as appropriate, in response to any entered BG values, just as if the BG values were CGM values.

The device also displays visual alarms, sounds audible alarms, and generates vibration alarms for problems with the functioning of the bionic pancreas.

Study teams will be trained by Beta Bionics on the use and implementation of the iLet. A delegation log reflecting training completion for study team members will be signed and maintained onsite.

5.4.4 *Ascensia Diabetes Care Contour Next One Glucose Meter system*

The Contour Next One glucometer is FDA approved and commercially available. Participants will be asked to use this meter and its proprietary test strips for all blood glucose measurements during the study.

5.4.5 *Precision Xtra Ketone Meter system*

The Precision Xtra ketone meter is FDA approved and commercially available. Participants will be asked to use this meter and its proprietary test strips for all blood ketone measurements during the study.

5.5 Screening and Randomization

5.5.1 Screening Visit (Visit 1)

At the screening visit, the following procedures will be performed:

- Informed consent
- Assessment of eligibility, including review of medications and medical history
- Recording of height and weight
- Urine pregnancy test for all post-menarche and premenopausal people who are not surgically sterile

A study MD or NP will review the case report form to determine eligibility. If participants are not eligible to continue in the study, the study MD or NP will explain why. Participants who have been screened and are eligible can participate without having to be re-screened for a period of 3 months. The study staff should verbally confirm that there have been no health events that would make them ineligible at every study visit and rescreen participants for eligibility if it has been greater than three months.

5.5.2 Prior to Randomization

- Psychosocial questionnaires (including quality of life, fear of hypoglycemia, diabetes distress).
- HbA1c assessment using a validated method (a value within 2 weeks prior to enrollment is acceptable)

5.5.3 Randomization of Study Arm Sequence

Participants will be recruited specifically into the in-person or telehealth cohorts, based on their circumstances. Once the participant has been enrolled and eligibility has been established, participants within each of these cohorts will be randomized to one of two possible study arm sequences.

5.6 Study Visit Procedures

5.6.1 Visit Procedures for in-person (IP) visits

5.6.1.1 Day 1 Visit (Visit 2):

- The body weight of the participant will be documented.
- A urine pregnancy test will be performed in participants of child-bearing potential at the start of the first arm. If the test is positive, the participant will be informed of the result and the visit will be ended. The date of the last menstrual period will also be documented.
- Study staff will review any changes in the participant's medical history or medications to ensure continued eligibility, and any adverse events that may have occurred since their screening visit.

5.6.1.1.1 Participants randomized to usual care:

- Study staff will provide supplies and review the study procedures.
- Participants will be trained how to insert, maintain and use the Dexcom G6 (in blinded mode if they are not a CGM user).
- The participants will wear a Dexcom G6 sensor and study staff will confirm they are doing it properly.

5.6.1.1.2 Participants randomized to bionic pancreas:

- Study staff will provide supplies and review the study procedures.
- Participants will be trained how to insert, maintain and use the Dexcom G6 CGM.
- The participants will wear a Dexcom G6 sensor and study staff will confirm they are doing it

properly.

- Participants will be trained to use the iLet, including navigating the GUI, filling and installing cartridges and inserting infusion sets.
- Participants will set up the iLet and insert the infusion set and study staff will confirm they are doing it properly.
- The control algorithm will be initialized with the participant's weight.
- If using an insulin pump (EN group), their own insulin infusion pump will be stopped and disconnected if applicable, and its infusion set will be removed
- If using MDI therapy (PC group), they will be instructed not to take any additional insulin injections once the bionic pancreas is started, unless instructed to do so by study staff
 - Participants on multiple daily injections (MDI) may be started on the iLet without a need for adjustment of their long-acting insulin dose. The new equilibrium will not be reached until all the long-acting insulin has completely cleared their system, which may take 48 hours or more. Participants must be advised that they may see escalating dosing by the iLet during this period.
 - Investigators may consider starting MDI users at the "higher" glucose target setting. If the "higher" setting is used, wait ~2 days before moving down to the default target.
- Participants will complete Clarke's Instrument for Impaired Awareness of Hypoglycemia.
 - Participants with a score > 4 will be instructed to check BG at 2am for the first 2 nights using the iLet

5.6.1.2 Mid-period Follow Ups (Visits 3, 4, 6, and 7):

- Study staff may supervise the first site change via a video visit, as needed or requested based on participant's prior experience and comfort level
- All participants will have a virtual phone visit on Day 2 and Day 5 (+/-2 days) to assess device adaptation, glucose control, and to answer any questions the participant may have
- Study staff will query the participant for any adverse events and assess the participant's ability to follow protocol and, if applicable, use the device at this time.

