- Supplies will be shipped to the participant in advance of the scheduled study start visit (Day 1 Visit immediately below). They will be instructed not to unpack any study materials until the scheduled telehealth visit. This will include a scale for measurement of weight, a home pregnancy testing kit, and supplies required for the study.
- All TH study visits will be completed using HIPAA compliant videoconferencing software.

5.6.2.1 Day 1 Visit (Visit 2):

- The body weight of the participant will be verbally self-reported by the participants, who will be instructed to use the scale provided.
- A urine pregnancy test in participants of child-bearing potential will be completed at home using the study-provided pregnancy test at the start of the first arm. Participants will be instructed to complete the pregnancy test during the virtual visit and to show result to study staff. If the test is positive, the participant will be informed of the result and the visit will be ended. The date of the last menstrual period will also be documented.
- Study staff will review any changes in the participant's medical history or medications to ensure continued eligibility, and any adverse events that may have occurred since their screening visit.

5.6.2.1.1 *Participants randomized to usual care:*

- Study staff will review supplies provided and the study procedures.
- Participants will be trained how to insert, maintain and use the Dexcom G6.
- The participants will wear a Dexcom G6 sensor and study staff will confirm they are doing it properly.

5.6.2.1.2 *Participants randomized to bionic pancreas:*

- Study staff will review supplies provided and the study procedures.
- Participants will be trained how to insert, maintain and use the Dexcom G6 CGM.
- The participants will wear a Dexcom G6 sensor and study staff will confirm they are doing it properly.
- Participants will be trained to use the iLet, including navigating the GUI, filling and installing

cartridges and inserting infusion sets.

- Participants will set up the iLet and insert the infusion set and study staff will confirm they are doing it properly.
- The control algorithm will be initialized with the participant's weight.
- If using an insulin pump (EN group), their own insulin infusion pump will be stopped and disconnected if applicable, and its infusion set will be removed.

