5.7.1 Policies for the Usual Care Arm

- Participants may be contacted between visits if needed, per the discretion of either the participant, a healthcare provider, or a member of the study team.
- The UC arm will continue its pre-study diabetes management, including approach to insulin delivery and management. Diabetes management will be handled by the participant's usual diabetes health care provider. *No adjustments to the diabetes care plan will be made by the study team.*

- Participants in the endocrinology (EN) cohort using FDA-approved devices as part of their pre-study usual care, such as a CGM system, insulin pump, or closed-loop system can continue use of their personal devices during the study period. Use of devices that are not FDA-approved is prohibited.

5.7.2 *Policies for the Bionic Pancreas Arms*

- Participants may be contacted between visits if needed, per the discretion of either the participant, a healthcare provider, or a member of the study team.
- Participants using the iLet will not be allowed to travel outside the United States or its territories for the entire time the system is in use.
- Participants may perform calibrations of the Dexcom G6 CGM if it is inaccurate relative to a BG measurement, per the device manufacturer's instructions.
- The iLet will have CGM glucose alarm settings available to the participants. Study staff will work with participants to configure the alarm settings in a way that will be most appropriate for each individual.
 - Study staff will recommend a low CGM glucose alarm be set for 75 mg/dl and a high CGM glucose alarm be set for > 300 mg/dl for 90 minutes.
- If participants receive a high or low CGM glucose alarm, they will be trained to verify the CGM glucose with a fingerstick glucose value using the Contour Next One glucometer.
 - The participant will be trained to treat hypoglycemia with rapid acting carbohydrates, in case the glucometer confirms hypoglycemia. This may be done according to their usual practice or with less carbohydrate than their usual practice since the BP system will typically have suspended insulin delivery prior to the occurrence of hypoglycemia. They will be trained to continue to monitor their glucose levels until they return to normoglycemia.

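### In the usual-care arm the study G6 is blinded only for people who are not CGM users, so users of another sensor may see it, and the telehealth visit list omits blinding

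*Combined protocol and SAP*

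**What the plan says.** All references are to the combined protocol and SAP.

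- **Who wears the study sensor.** Everyone in usual care. The in-person steps (5.6.1.1.1) state "The participants will wear a Dexcom G6 sensor and study staff will confirm they are doing it" properly, and the telehealth steps (5.6.2.1.1) say the same.
- **In-person display rule (5.6.1.1.1).** The step that trains participants to place, look after and use the G6 adds "in blinded mode if they are not a CGM user".
- **Device section (5.4.2).** "In the PC group, if the participant is not a CGM user the CGM will be blinded". It is not tied to a visit mode or to an arm.
- **Telehealth steps (5.6.2.1.1).** "Participants will be trained how to insert, maintain and use the Dexcom G6", with nothing about blinding.
- **Personal devices (5.7.1).** EN participants with FDA-approved equipment "can continue use of their personal devices during the study period".
- **Intent of the arm (5.7.1).** "The UC arm will continue its pre-study diabetes management, including approach to insulin delivery and management".
- **Alarms (5.7.3).** The blinded CGM has none, and users of a personal CGM follow their own provider's settings. An unblinded study G6 is not mentioned.
- **Sensor type.** CGM type is recorded at screening (5.2, 6.1.1). No eligibility criterion requires it to be a G6.

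**The concern.** The display rule turns on whether a person uses any CGM. For keeping usual care as it was, the relevant question is whether the study G6 shows that person something they did not see before. The two questions give the same answer for people without CGM and for people whose own sensor is a G6. They give different answers for someone whose own sensor is another make or type. That person counts as a CGM user, so nothing blinds the study G6.

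The usual-care arm feeds three things: the paired iLet-versus-usual-care comparisons within groups (6.7), the hypothesis that this difference is larger in PC than in EN (2.2), and the psychosocial comparison of the two arms (2.2). Section 2.2 also says the glycemic data will be used to power a larger study, so a distorted difference would be carried forward.

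**Working it through.** **1. Apply each rule to each type of usual-care participant.** EN entry requires sensor-augmented pump or artificial pancreas therapy (3.1, criterion 3). All 20 planned EN participants are therefore CGM users.

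| Participant | 5.4.2 | 5.6.1.1.1 (in person) | 5.6.2.1.1 (telehealth) |
|---|---|---|---|
| PC, no CGM | blinded | blinded | not mentioned |
| PC, own sensor is a G6 | no blinding | no blinding | not mentioned |
| PC, own sensor is not a G6 | no blinding | no blinding | not mentioned |
| EN, own sensor is a G6 | no blinding | no blinding | not mentioned |
| EN, own sensor is not a G6 | no blinding | no blinding | not mentioned |

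The two rows for another sensor are the gap. The first row is a wording inconsistency. It concerns the non-users among the 10 planned PC telehealth participants, whom 5.4.2 says to blind and whose own visit list does not. Section 5.6.2.3 sends participants back to the Day 1 steps at crossover, so both sequences use that list.

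**2. Is there a precedent in the documents?** Yes. In the Beacon Hill Study (Appendix A, 12.1.2), control participants kept their own CGM if they had one. They also wore a study sensor whose display was hidden and whose alarms were silenced. That is the arrangement missing here.

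**3. Can extra glucose surveillance change usual care and leave the device arms unchanged?** In the Monitoring Study (12.1.5), usual-care hypoglycemia was 1.95% without remote monitoring and 1.32% with it (p=0.02). No difference was detected with the bihormonal device (0.99 v 1.05%, p=0.82) or the insulin-only device (1.66 v 1.55%, p=0.74). Remote monitoring by staff is not a second display, so this supports the mechanism only and gives no size.

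**4. Size.** The plan has no figure to reproduce, because 6.6 reports no power or sample size calculation. The shift in a group's usual-care mean glucose is

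shift = f × e,

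where f is the share of the group with a visible study G6 that is new to them, and e is the mean fall in their glucose because of it. The documents give neither. The values below are assumptions, to show the spread (mg/dl):

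| f | e = 2 | e = 5 | e = 10 |
|---|---|---|---|
| 0.10 | 0.2 | 0.5 | 1.0 |
| 0.25 | 0.5 | 1.25 | 2.5 |
| 0.50 | 1.0 | 2.5 | 5.0 |
| 1.00 | 2.0 | 5.0 | 10.0 |

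The scale to set this against is itself unstable. Usual care minus insulin-only device, in adults (Tables 1 and 2):

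- Bridging Study: 163 − 155 = 8 mg/dl
- Stanford study: 151 − 160 = −9 mg/dl
- Monitoring Study with monitoring: 164 − 151 = 13 mg/dl
- Monitoring Study without monitoring: 165 − 148 = 17 mg/dl

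Against 8 mg/dl, the table runs from 0.2/8 = 2.5% to 10/8 = 125%. With the Bridging usual-care SD of 26, the standard error of one usual-care mean is 26/√10 = 8.2 mg/dl for a group of 10 and 26/√20 = 5.8 mg/dl for 20. Most of the assumed shifts are smaller than that. A bias, however, does not shrink as a later trial gets larger.

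**5. Direction.** Write D for usual care minus iLet. If e is positive, each group's D falls by its own f × e. Then

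observed (D_PC − D_EN) = true (D_PC − D_EN) − (f_PC·e_PC − f_EN·e_EN).

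More contamination in EN exaggerates the hypothesized PC advantage, and more in PC hides it. The sensor mix is not given, so the sign is unknown.

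**6. Primary endpoint.** Section 6.7 estimates the percentage below 183 mg/dl in the iLet arms of the four groups. Usual-care data do not enter.

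**The case against.** The strongest reply is that this is a small ambiguity in a feasibility trial. Several parts of it stand.

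- **The visible second display is inferred.** No section says that users of another sensor see the study G6. The documents set blinded mode for non-users and are silent on everyone else. Being trained to use the G6 proves nothing, because the in-person sentence applies the same verb to blinded wear.
- **A reader might infer that the comparator is no longer usual care.** The documents do not support that. Those affected already use CGM, EN participants may keep their own devices, and the study team changes no dosing regimen or care plan (5.6.1.2.2, 5.6.2.2.2, 5.7.1). At most, some people see a second reading.
- **A reader might see a conflict with exclusion 4a.** That criterion concerns a plan to change regimen, including "starting a CGM if not previously used". It does not describe someone already using a CGM.
- **A reader might infer that telehealth non-users are meant to be unblinded.** Section 5.4.2 covers PC non-users in either visit mode, and 5.7.3 also assumes a blinded CGM. The telehealth list omits the instruction but does not contradict it.
- **Little rides on it formally.** The primary estimate is untouched, and p-values are not for inference (6.7). Exploratory stratification by CGM use in usual care is foreseen.

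Two parts do not dispose of the point. Stratifying by CGM use does not separate G6 users from users of other sensors, which is the split that matters. And silence on display mode leaves each site to decide, so usual care could differ by group and by visit mode.

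**Conclusion.** The point holds as a gap in the display rule. Blinding depends on using no CGM at all, so a participant whose own sensor is not a G6 may wear an unblinded study G6 beside it. The telehealth list also lacks an instruction that 5.4.2 requires for PC non-users.

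The consequence is possible contamination of usual care in a subset of unknown size. If the extra display improves control, the secondary iLet-versus-usual-care differences shrink. The PC-versus-EN comparison of those differences could then move either way. Both statements rest on two things the documents do not give: how many participants use another sensor, and what a second display does for someone already on CGM. The table of assumed values shows only that the shift could be negligible or material. It should not be quoted as an estimate, and a reader should not attach a mg/dl figure to the bias.

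The primary endpoint is unaffected. This is an inexpensive improvement to the secondary comparisons and does not threaten the trial's main result.

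**What to change.** Use one rule, in the same words, in 5.4.2, 5.6.1.1.1 and 5.6.2.1.1, for both sites and both visit modes: in the usual-care arm the study G6 is blinded, with no alarms, unless a Dexcom G6 is already the participant's own usual-care sensor. Participants with another personal CGM keep it as their visible sensor.

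- Name the usual-care arm in 5.4.2, which at present names no arm.
- Apply the rule from the CGM type already recorded at screening (5.2, 6.1.1).
- Section 5.7.3 already says the blinded CGM has no alarms, so it would then cover these participants too.
- Summarize usual-care results by personal sensor type. The data are already collected.

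The cost is a wording amendment and a few more blinded set-ups. Blinded mode is already in use in the trial, and participants' own monitoring does not change.
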